3.4 Inclusion criteria

(1) Newborns who underwent genetic screening and tandem mass spectrometry at the same time.

(2) Age : 0-28 days, gestational age 37-42 weeks.

3.5 Excluded criteria

Data that meets any of the following conditions need to be eliminated :

(1) Neonatal data with unclear clinical basic information ;

(2) Lack of traceability core information data ;

(3) The data that the test results cannot be analyzed and interpreted.

3.6 Observation items

(1) Positive detection rate of common genetic diseases in neonates : the results of genetic testing of enrolled neonates showed that the proportion of homozygous and compound heterozygotes of autosomal recessive inheritance, single heterozygote and homozygous of autosomal dominant inheritance, and hemizygote of X-linked inheritance accounted for the total number of people tested.

(2) The corresponding pathogenic genes and pathogenic variation carrying rate of common neonatal genetic diseases : that is, the proportion of the total number of occurrences of pathogenic variation, suspected pathogenic variation and

unknown clinical significance variation in the genetic test results of the enrolled neonates according to the ' ACMG genetic variation classification criteria and guidelines ' and ' genetic variation classification criteria and guidelines (2017) '.

- (3) The carrying rate of high-frequency mutation sites in the population : that is, the mutation sites with a population carrying rate greater than 1 %.
- (4) Establish a complete protein structure and catalytic activity analysis process, and develop artificial intelligence protein analysis tools for pathogenicity prediction of mutation sites.
- (5) Preliminary identification of the pathogenicity of high-frequency VUS mutation sites : The protein structure and enzyme catalytic activity characteristics of high-frequency VUS mutation sites were predicted by artificial intelligence tools, and the metabolic spectrum differences between positive, carrier and negative samples of high-frequency VUS mutation sites were clarified by combining with tandem mass spectrometry metabolite data, which provided a basis for the pathogenicity judgment of VUS mutation.
- (6) Gene-metabolism correlation : machine learning algorithms such as random forest, support vector machine, elastic network and multi-layer perceptron are used to construct prediction models of common genetic diseases, so as to realize accurate diagnosis of common genetic diseases through tandem mass spectrometry metabolomics data, and expand 2-3 diseases that can be diagnosed by tandem mass spectrometry.

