research object	Gene screening data of 40,000 newborns (138 genes related to 133 common genetic diseases) and tandem mass spectrometry data (11 amino acids and 28 acylcarnitines).
Inclusion criteria	(1) Newborns who underwent genetic screening and tandem mass spectrometry at the same time. (2) Age : 0-28 days, gestational age 37-42 weeks.
Excluded criteria	Data that meets any of the following conditions need to be eliminated : (1) Neonatal data with unclear clinical basic information ; (2) Lack of traceability core information data ; (3) The data that the test results cannot be analyzed and interpreted.
sample size	Gene screening and tandem mass spectrometry data of 40,000 newborns.
data collection	(1) Basic information : gender, age, sample type, subject traceability number / ID number, etc. (2) Clinical symptoms, biochemical and imaging data of positive samples. (3) Gene detection results and tandem mass spectrometry results.

	(4) Date of test data, instrument model, reagent type, etc.
Statistical processing	IBM-SPSS 26.0 statistical software was used to analyze the test results. Logistic regression analysis was used to evaluate the correlation between genotype and clinical phenotype. Generalized multifactor dimensionality reduction method was used to analyze gene-gene interaction and genotype-phenotype correlation. Based on tandem mass spectrometry data, machine learning algorithms such as random forest, support vector machine, elastic network, and multi-layer perceptron were used to construct a genotype prediction model. The prediction effect of the model was evaluated by accuracy, balance accuracy, sensitivity, and specificity.
abbreviation	Principal Investigator, PI; tandem mass spectrometry, MS/MS; Inborn errors of metabolism, IEM

1. project basis

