model was applied to the diagnosis of common pediatric diseases. The results showed that the diagnostic accuracy of 55 common pediatric diseases was close to 90 %. Some diseases such as acute upper respiratory tract infection had a diagnostic accuracy of 95 %, and the average score of the artificial intelligence model was higher than that of the doctor group. Therefore, artificial intelligence can assist early disease diagnosis through a large amount of medical data, improve diagnosis efficiency and reduce misdiagnosis rate, solve the problem of insufficient medical service capacity to a certain extent, and improve the fairness and accessibility of health services. In the field of neonatal disease screening, with the promotion of genetic screening technology and the inclusion of more genetic metabolic diseases in screening, accurate and rapid judgment of multiple disease risks has become an urgent need for clinical front-line. Artificial intelligence has obvious advantages in the interpretation and risk prediction of genetic metabolic disease gene results, which not only significantly reduces the false positive results and saves medical resources ; for areas with weak clinical foundation and urgent need to carry out neonatal genetic metabolic disease gene screening projects, artificial intelligence tools will become a strong support for clinicians, promote the standardization and standardization of genetic metabolic disease diagnosis, and improve the efficiency and accuracy of neonatal genetic metabolic disease gene screening system.

According to the preliminary development of neonatal genetic screening in China, we will retrospectively collect and analyze the genetic screening data and tandem mass spectrometry data of 40,000 newborns in the participating units of the South China Neonatal Genetic Screening Alliance, so as to understand the incidence of neonatal genetic diseases in China and the characteristics of the carrying rate and mutation sites of related gene pathogenic variations, and provide scientific research basis for the feasibility, clinical value and social benefits of large-scale genetic screening. In addition, our previous studies have found that the mutation sites with high carrying rate (more than 1 %) in many populations are mutations of unknown clinical significance (VUS). The pathogenic interpretation of such mutations has brought serious confusion to clinicians and brought pending trouble to the subjects.

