3.1 Sample size

This study plans to collect genetic screening data (138 genes related to 133 common genetic diseases) and tandem mass spectrometry metabolomics data (11

amino acids and 28 acylcarnitines) of about 40,000 newborns from January 2019 to August 2022 in 123 cooperative units of the South China Neonatal Genetic Screening Alliance.

3.3 data collection

In the course of the study, no random or any treatment driven by the research program will be performed or provided to the subjects. The researchers will view the patient 's medical history and laboratory reports, and determine the patient 's eligibility according to the inclusion and exclusion criteria.

(1) The types of diseases detected by genetic screening : including 133 kinds of hereditary diseases with high incidence in neonates. The types of diseases include genetic metabolic diseases such as amino acid metabolic diseases, organic acid metabolic diseases and fatty acid metabolic diseases within the scope of all neonatal tandem mass spectrometry screening, as well as other genetic diseases that cannot be screened by tandem mass spectrometry but have high incidence and early detection of great clinical significance and social benefits for children and families, such as lysosomal diseases, glycogen accumulation diseases, hepatolenticular degeneration, hereditary deafness, β -thalassemia, etc.

(2) In this study, the data analysis of genes and the interpretation of test reports are based on the implementation of industry consensus or guidelines for genetic testing of genetic diseases such as ' Discussion on the standardized consensus of the whole process of clinical detection of genetic diseases second-generation sequencing '. The analysis and interpretation of test data refer to the ' ACMG genetic variation classification criteria and guidelines ' issued by the American Society of Medical Genetics and Genomics (ACMG) in conjunction with the Molecular Pathology Society (AMP) and the domestic ' genetic variation classification criteria and guidelines (2017) '. The variation was divided into five grades : pathogenic (P, pathogenic possibility > 0.99), suspected pathogenic (LP, pathogenic possibility 0.95-0.99), unknown clinical significance (VUS, pathogenic possibility 0.01-0.90), suspected benign (LB, pathogenic possibility

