3.7 Statistical processing

IBM-SPSS 26.0 statistical software and R language (Version 4.1.0) were used for statistical analysis of the test results, and the positive rate of neonatal genetic disease screening (common positive disease cases, common positive sites) was counted. The carrying rate of common mutation sites in newborns was counted. The measurement data were expressed as mean \pm standard deviation ($x \pm s$), and t test was used for comparison between groups. The count variables were expressed as values or rates (%), and the comparison between groups was tested. Unconditional logistic regression analysis was used to evaluate the correlation between genotype and

clinical phenotype. Generalized multifactor dimensionality reduction (GMDR) was used to analyze gene-gene interaction and genotype-phenotype correlation. Based on tandem mass spectrometry data, machine learning algorithms such as random forest, support vector machine, elastic network, and multi-layer perceptron were used to construct genotype prediction models. Accuracy, Balanced accuracy, sensitivity, and specificity were used to evaluate the prediction effect of the model.

4. Ethics in clinical research

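### The metabolite comparison for high-frequency VUS has no reference from sites of known pathogenicity and no minimum difference, so shifts of about 0.1 SD can reach significance without showing what they mean

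*Combined protocol and SAP*

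**What the plan says.** Section 3.6 item (3) defines high-frequency sites as "the mutation sites with a population carrying rate greater than 1" per cent. Item (5), labelled preliminary, describes two strands of evidence for the VUS among them:

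- A prediction: "The protein structure and enzyme catalytic activity characteristics of high-frequency VUS mutation sites were predicted by artificial intelligence tools".
- A metabolite comparison: "the metabolic spectrum differences between positive, carrier and negative samples of high-frequency VUS mutation sites were clarified".

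Together these are described as something "which provided a basis for the pathogenicity judgment of VUS mutation". Objective (3) in section 2 adds a filter: characteristic metabolites are examined at sites where enzyme activity is low. No cut-off for low activity is given.

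For measurement data, section 3.7 offers one between-group method: "t test was used for comparison between groups". It states no significance level, minimum difference, multiplicity rule or rule for turning a result into a pathogenicity statement.

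Section 3.3 item (2) sets out the ACMG-based grading: "The variation was divided into five grades". Only P and LP count there as positive mutations, and VUS are not to be used directly for diagnosis. Nowhere are the P/LP or B/LB sites used as a reference for the VUS comparison.

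**The concern.** A test against zero asks whether the groups at a VUS site differ at all. The question in item (5) is whether they differ in the way that groups at a pathogenic site differ and groups at a benign site do not. In a dataset of this size the two questions can have different answers.

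The plan's own background (section 1.1) shows why the result is hard to read in either direction:

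- It says biochemical screening results are affected by gestational age, birth weight, nutrition and medication, so a small shift is not specific to pathogenicity.
- It names diseases in which metabolites are usually normal in newborns, so the absence of a shift is not evidence that a variant is benign.

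At stake is one of the main aims. Sections 1.1 and 1.2 speak of resolving the pathogenicity of VUS, finding high-risk children and lowering false positives, and objective (3) asks whether pathogenicity can be predicted accurately. Accuracy cannot be shown without sites of known status.

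**Working it through.** **Inputs from the documents**

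- Newborns: about 40,000 ("Gene screening and tandem mass spectrometry data of 40,000 newborns", abstract). This is a number of records to collect. No power, effect size or SD accompanies it, so there is no sample-size calculation to reproduce.
- High-frequency threshold: carriage above 1% (3.6 item 3), with no upper limit and no list of sites.
- Analytes: 11 amino acids + 28 acylcarnitines = 39.

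**Assumptions**

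- Two-sided 5% level, equal SDs and a normal approximation.
- Carriage of 2% and 5% shown as a range above the documented 1% floor.
- Hardy-Weinberg proportions for homozygotes.

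**Step 1. Carriers.** 40,000 × 0.01 = 400, so each high-frequency site has more than 400. At 2% there would be 800, at 5% 2,000.

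**Step 2. Size of shift, in SD units.** SE = √(1/n₁ + 1/(40,000 − n₁)). The smallest significant difference is 1.960 × SE. The difference with 80% power is (1.960 + 0.842) × SE = 2.802 × SE.

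| Carriage | Carriers vs others | SE | Just significant | 80% power | Power for 0.1 SD |
|---|---|---|---|---|---|
| 1% (floor) | 400 vs 39,600 | 0.0503 | 0.099 | 0.141 | 51% |
| 2% (assumed) | 800 vs 39,200 | 0.0357 | 0.070 | 0.100 | 80% |
| 5% (assumed) | 2,000 vs 38,000 | 0.0229 | 0.045 | 0.064 | 99% |

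**Step 3. What such shifts mean.** Overlap of two normal distributions d SD apart = 2Φ(−d/2). This gives 97% at d = 0.064, 96% at d = 0.099 and 94% at d = 0.141. The corresponding AUC, Φ(d/√2), is 0.53 at 0.099 and 0.54 at 0.141, close to chance.

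**Step 4. Number of analytes.** If all 39 were tested at 5%, 39 × 0.05 = 1.95 false positives per site would be expected under the null. The chance of at least one would be 1 − 0.95³⁹ = 86% if they were independent. Restriction to characteristic metabolites lowers this, but their number is not stated. Bonferroni over 39 raises the significance threshold only to 0.162 SD at 400 carriers and 0.074 SD at 2,000, so multiplicity control does not supply the missing reference.

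**Step 5. The third group.** If positive means homozygous for the VUS, 1% carriage gives an allele frequency q = 1 − √0.99 = 0.00501 and 40,000 × q² ≈ 1 homozygote. At 2% about 4 are expected and at 5% about 26. Near the threshold, the carrier-versus-negative contrast does almost all the work.

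**The case against.** The plan does more than compare carriers with negatives, and a fair reading must allow for that.

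- **Three groups.** A positive group is included. If positive keeps its meaning from 3.3 item (2), a known-pathogenic comparator is partly present. If it means VUS homozygotes, there is a dose-response contrast. The text does not say which. Under the first reading there is still no benign reference and no statement that effect sizes are compared; under the second the group is nearly empty near 1% carriage.
- **Filter and AI prediction.** A shift has to be in a relevant analyte at a site with low enzyme activity. This does narrow the scope for chance findings. But the filter has no cut-off and no check of the AI tool on sites of known status is described. The validation in 3.3 item (4) concerns the risk model and compares its output with the original screening results, not P/LP with B/LB sites.
- **Modest claims.** A reader might infer that benign variants will be upgraded on the strength of p < 0.05. The documents do not support that: there is no decision rule, item (5) is preliminary, objective (3) explores feasibility, and VUS are not used directly for diagnosis. The plan permits such a reading without prescribing it.
- **Group sizes.** A reader might also infer that nearly any difference will be significant, for instance with 4,000 carriers. That needs 10% carriage, which the documents do not give. At 400 carriers a 0.1 SD shift has only 51% power.
- **Availability of controls.** It is tempting to say both references are already in hand. Section 3.6 item (2) counts only P, LP and VUS, and nothing says that B/LB calls are kept in the transferred tables.

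These points limit the concern. None of them supplies a reference from sites of known status.

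**Conclusion.** The point holds as a gap in calibration. The plan judges high-frequency VUS from genotype-group differences in metabolites, together with an AI prediction and a low-activity filter, without a reference from known P/LP or B/LB sites and without a minimum difference. At the documented floor of 400 carriers, about 0.1 SD is enough for significance and 0.14 SD has 80% power; at an assumed 5% carriage the latter falls to 0.064 SD. Groups that far apart overlap by 94% to 97%. A significant result could therefore be taken as evidence of pathogenicity, and a null result says nothing about benignity in genes where newborn metabolites are usually normal.

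The figures rest on a two-sided 5% level and on carriage rates above 1%, neither of which the plan states. That variants will in fact be misclassified is not shown. The change is worth making, and because the work is preliminary and VUS do not feed directly into diagnosis, it is a recommended improvement and not a fatal defect.

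**What to change.** Add a paragraph to 3.6 item (5) and 3.7 that does the following:

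1. Says what positive means at a VUS site.
2. Runs the same comparison (same characteristic metabolites, genotype groups and adjustment) at the known P/LP sites of the same genes and, where those calls are held, at B/LB sites. Grades must be assigned without these MS/MS data, to avoid circularity.
3. Uses metabolites to judge a VUS only in genes where P/LP sites separate from B/LB sites, or from negatives if B/LB calls are not held. In the latter case only the pathogenic end is calibrated, and the report should say so.
4. Reports each VUS effect size with its interval against those reference effects, and not only as significance against zero.
5. Scores the AI tool on the same control sites.

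The cost is added analysis with no new samples or assays, plus confirmation from the participating units that B/LB calls were retained. Genes with too few control sites would have to be reported as not assessable, which may reduce the number of VUS on which the study can comment.

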3.7 Statistical processing

IBM-SPSS 26.0 statistical software and R language (Version 4.1.0) were used for statistical analysis of the test results, and the positive rate of neonatal genetic disease screening (common positive disease cases, common positive sites) was counted. The carrying rate of common mutation sites in newborns was counted. The measurement data were expressed as mean \pm standard deviation ($x \pm s$), and t test was used for comparison between groups. The count variables were expressed as values or rates (%), and the comparison between groups was tested. Unconditional logistic regression analysis was used to evaluate the correlation between genotype and

clinical phenotype. Generalized multifactor dimensionality reduction (GMDR) was used to analyze gene-gene interaction and genotype-phenotype correlation. Based on tandem mass spectrometry data, machine learning algorithms such as random forest, support vector machine, elastic network, and multi-layer perceptron were used to construct genotype prediction models. Accuracy, Balanced accuracy, sensitivity, and specificity were used to evaluate the prediction effect of the model.

4. Ethics in clinical research

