How to accurately analyze the pathogenicity of a large number of high-frequency VUS mutations has become a key problem to be solved in neonatal genetic screening. Therefore, we intend to use 40,000 cases of gene screening data and tandem mass spectrometry data, and establish a risk assessment model for neonatal genetic metabolic disease gene screening results through protein function artificial intelligence method, in order to solve the pathogenicity problem of high-frequency VUS and provide reliable research basis for clinical practice, so as to quickly and accurately identify high-risk children, reduce the false positive rate of gene screening, and improve the accuracy and system efficiency of neonatal gene screening.

In addition, we will also explore the use of neonatal gene screening data and tandem mass spectrometry data, as well as machine learning algorithms such as random forest, support vector machine, elastic network, and multi-layer perceptron to construct prediction models for common genetic diseases, and strive to achieve accurate diagnosis and prediction of common genetic diseases using simple tandem mass spectrometry metabolomics data, and expand the application range of tandem mass spectrometry technology for disease detection.

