(2) A retrospective analysis of the incidence, pathogenic mutations, suspected pathogenic mutations, and the carrying rate of unexplained mutations of 133 common neonatal genetic diseases in 40,000 cases was conducted, and the distribution of high-frequency variation sites in the population was counted, providing a scientific basis for the selection of mutation sites for large-scale genetic screening of neonatal genetic diseases.

(3) Protein function prediction and enzyme catalytic activity analysis were performed on high-frequency mutation sites of genetic metabolic diseases (IEM). Characteristic metabolites were analyzed and verified for mutation sites with low enzyme catalytic activity. The feasibility of using protein function artificial intelligence analysis platform and tandem mass spectrometry metabolite data to accurately predict the pathogenicity of genetic metabolic lesions was explored.

(4) Explore the use of genome and metabolome big data and machine learning algorithms such as Random forest, Support Vector Machine, Elastic net, Multilayer Perceptron to construct prediction models for common genetic diseases, and strive to achieve accurate diagnosis and prediction of common genetic diseases using simple

tandem mass spectrometry metabolome data, and expand the application range of tandem mass spectrometry technology for disease detection.

3. Research scheme and technical route

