3.1 Research Design

This study is a multi-center cooperative study of the South China Neonatal Genetic Screening Alliance. The principal investigator (PI) and project leader of this study are [name], chief physician of pediatrics of the Sixth Affiliated Hospital of Sun Yat-sen University, who plans to include 123 cooperative units of the South China Neonatal Genetic Screening Alliance. In this study, 40,000 neonatal genetic screening data and MS / MS data were retrospectively analyzed through multi-center cooperation. The collection date was from January 2019 to August 2022.

Through the statistical analysis of neonatal genetic screening data (138 genes related to 133 common genetic diseases), the incidence of common genetic diseases in newborns in China, the carrying rate of pathogenic variation and the high-frequency variation sites of the population were clarified, and the epidemiological characteristics of newborns in China were studied.

Through the statistical analysis of neonatal genetic screening data and MS / MS metabolomics data (11 amino acids and 28 acylcarnitines), the correlation between gene and metabolism will be explored, and the pathogenicity of high-frequency VUS mutation sites will be identified by using protein function artificial intelligence analysis platform and tandem mass spectrometry metabolite data.

The prediction model of common genetic diseases is constructed by using machine learning algorithms such as random forest, support vector machine, elastic network and multi-layer perceptron, so as to realize the accurate diagnosis of common genetic diseases through tandem mass spectrometry metabolomics data, and expand 2-3 kinds of diseases that can be detected by MS / MS technology.

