0.001-0.01), benign (B, pathogenic possibility < 0.001). The results of gene detection in this study only classified pathogenic and possible pathogenic mutations as positive mutations, and homozygotes and compound heterozygotes of autosomal recessive inheritance, single heterozygotes and homozygotes of autosomal dominant inheritance, and hemizygotes of X-linked inheritance were classified as disease positive. The unclear clinical significance is not directly used as the basis for clinical diagnosis. It is necessary to combine the clinical, if necessary, to carry out the corresponding family member verification, auxiliary examination, clinical follow-up.

(3) MS / MS data collection and standardization : The collected data include (1) laboratory background information including instrument type, reagent type, quality control material type, laboratory quality control rules, filter paper type, normal population range ; (2) Quality control data included quality control number, quality control type, quality control batch number, amino acid internal standard batch number, acylcarnitine internal standard batch number, factory time, experimental time, and test value of each quality control analyte ; (3) Screening test data include screening number, gestational age, breastfeeding method, native place (province, city), newborn gender, birth date, birth weight, sample number, blood collection time, etc. ; (4) The data of confirmed cases included screening number, confirmed disease, blood ammonia test, blood gas analysis, blood routine, liver function test, urine GC-MS test, imaging examination, gene detection information and other tests. The fluctuation range of the detection concentration of the corresponding batch of quality control samples was within the target value ± 3 s. Finally, the data were collected and sorted into the negative database and the positive database. In order to eliminate the influence of regional differences, the series detection index data were standardized.

(4) By analyzing the correlation between large sample gene data and tandem mass spectrometry data and the correction of clinical prognosis, a neonatal genetic disease gene screening database and an artificial intelligence risk assessment

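### The metabolite comparison at high-frequency VUS sites (section 3.6 item 5) defaults to an unadjusted two-group t test, with the positive group undefined and no significance level or multiplicity rule

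*Combined protocol and SAP*

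**What the plan says.** Section 3.6 item (5) states that "the metabolic spectrum differences between positive, carrier and negative samples of high-frequency VUS mutation sites were clarified", in combination with artificial-intelligence prediction of protein structure and enzyme activity, as a basis for judging pathogenicity. Section 3.1 (Research Design) puts the aim more firmly: "the pathogenicity of high-frequency VUS mutation sites will be identified by using protein function artificial intelligence analysis platform and tandem mass spectrometry metabolite data". Section 5 schedules this preliminary identification as an output for 2023–2024.

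Section 3.7 does not mention item (5), VUS sites or the three groups. For measurement data it gives mean and standard deviation, "and t test was used for comparison between groups". Logistic regression is listed for genotype and clinical phenotype, and "Generalized multifactor dimensionality reduction (GMDR) was used to analyze gene-gene interaction and genotype-phenotype correlation"; neither has named covariates. The machine learning models predict genotype from metabolites and serve item (6).

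Section 3.3 item (2) defines positivity: "The results of gene detection in this study only classified pathogenic and possible pathogenic mutations as positive mutations". It then sets zygosity rules by inheritance mode: biallelic genotypes for recessive disease, while "single heterozygotes and homozygotes of autosomal dominant inheritance, and hemizygotes of X-linked inheritance were classified as disease positive".

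Research objective (3) narrows the metabolite work: "Characteristic metabolites were analyzed and verified for mutation sites with low enzyme catalytic activity". It does not list those metabolites.

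**The concern.** Three things needed to run item (5) are missing.

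(a) **Groups.** A VUS is by definition not in the pathogenic or likely pathogenic class, so the section 3.3 rule leaves *positive* without a meaning at a VUS site. The three-way split also fits only recessive inheritance. Under the plan's own zygosity rules a single dominant heterozygote is already disease positive, and a male cannot be an X-linked carrier in this sense.

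(b) **Adjustment.** Section 1.1 says that biochemical screening results depend on gestational age, birth weight, nutrition, medication and environment. Section 3.3 item (3) collects several of these, plus birth date, blood collection time, sex, native place, instrument type and reagent type. No analysis uses any of them.

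(c) **Error control.** There is no significance level and no rule for multiple analytes, contrasts or sites.

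With these left open, the weight given to a large, sensitive carrier contrast against a possibly sparse homozygote contrast would be settled after the data are seen.

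**Working it through.** The plan gives no power, effect size or error rate for item (5), so there is no figure of its own to reproduce. The steps below size the gaps.

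**Inputs from the plan:** about 40,000 newborns; 11 amino acids + 28 acylcarnitines = 39 analytes; high frequency means a carrying rate above 1% (section 3.6 item 3). **Assumptions:** two-sided 5% per test; Hardy-Weinberg proportions; carrying rate c read as heterozygote frequency.

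**1. Homozygotes at a recessive site.** Solve 2q(1−q) = c, so q = (1 − √(1−2c))/2. Expected homozygotes = 40,000 × q².

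| c | q | Expected homozygotes | Poisson chance of fewer than 5 |
|---|---|---|---|
| 1% | 0.005025 | 1.0 | 99.6% |
| 2% | 0.01010 | 4.1 | 61% |
| 3% | 0.01523 | 9.3 | about 5% |
| 5% | 0.02566 | 26 | negligible |
| 10% | 0.05279 | 111 | negligible |

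At 1% the chance of no homozygote at all is exp(−1.01) = 36%.

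**2. Effect of the missing definition at 1% carriage.** Applying the section 3.3 rule literally gives 0 positives. Counting homozygotes gives about 1. Adding compound heterozygotes gives 2 × q × r × 40,000 more, where r is the total frequency of other qualifying alleles. The documents do not give r. For assumed r of 0.5%, 1% and 2% this adds 2.0, 4.0 and 8.0, for totals of about 3, 5 and 9.

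**3. Carrier contrast at 1%.** There are 400 carriers and 40,000 − 400 − 1 = 39,599 non-carriers. The standard error in SD units is √(1/400 + 1/39,599) = 0.0503. The smallest significant observed difference is 1.96 × 0.0503 ≈ 0.10 SD.

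**4. X-linked site, for contrast.** With half the newborns male and 1% overall carriage, (q + 1 − (1−q)²)/2 = 0.01 gives q = 0.00668, so 20,000 × q ≈ 134 hemizygous males. Sparseness is therefore a feature of recessive sites near the threshold, not of item (5) in general.

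**5. Multiplicity.** Testing all 39 analytes gives 39 × 0.05 = 1.95 expected false positives per null contrast per site. All three pairwise contrasts would give 3 × 1.95 = 5.85. These expected counts do not depend on how the analytes are correlated. The number of sites is not stated.

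**6. What already limits confounding.** Eligibility at 37–42 weeks (section 3.4) narrows gestational age but no other factor, and postnatal age still runs from 0 to 28 days. Section 3.3 item (3) standardises analytes for regional differences by an unstated method and applies a quality-control range of ±3 s. Neither addresses birth weight, feeding or age at blood collection.

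**The case against.** The strongest replies each carry some weight.

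*The t test is a general rule, so item (5) does have a method.* Agreed as a default reading. But it is a two-group test for three groups, without covariates. Nor is it the plan's only use of continuous data: the prediction models also use the metabolite values, for item (6).

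*Positive has a workable meaning.* Section 3.6 item (1) describes positivity by zygosity without repeating the pathogenic/likely pathogenic limit. This is a possible reading, but it does not say which second alleles make a compound heterozygote positive, and step 2 shows that this matters.

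*A factor that affects metabolites does not bias the comparison unless it differs by genotype.* Correct. A reader might infer that the comparison is confounded, but the documents show no imbalance. Any imbalance would arise mainly through region, ancestry or laboratory, which the standardisation covers in part. Birth weight, gestational age and feeding could also lie on the path from genotype to metabolite, so adjusting for them is not automatically right.

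*Not all 39 analytes will be tested at every site.* Probably so. Research objective (3) points to characteristic metabolites at sites for inborn errors of metabolism (IEM) with low predicted enzyme activity. Section 1.1 says "How to accurately analyze the pathogenicity of a large number of high-frequency VUS mutations has become a key problem to be solved", but that is background, not a count for this study.

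*The work is preliminary.* True. Section 3.3 also bars a VUS from direct use as a basis for clinical diagnosis. A reader might infer that a significant carrier difference alone will be called pathogenic; no section says that.

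**Conclusion.** The point holds as a gap in specification that should be closed before analysis. Groups, covariates, significance level and multiplicity rule are all unstated for a named study output, and the default method does not match the comparison.

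Its size is bounded. The 1.95 false positives per null contrast per site is an upper limit that assumes all 39 analytes are tested at 5%. The homozygote contrast is too sparse for a t test only near the 1% floor: about 1 and 4 expected at 1% and 2%, but 9, 26 and 111 at 3%, 5% and 10%, under Hardy-Weinberg. At that floor the carrier contrast is significant from about 0.10 SD, so even a small residual imbalance could matter there. Whether such an imbalance exists cannot be told from the documents. A reader might infer that item (5) is unworkable at high-frequency sites generally; the counts do not support that.

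**What to change.** In section 3.7, replace the t test for item (5) with linear regression of each analyte on genotype group, limited to IEM genes that have a mass spectrometry marker. Section 3.3 includes diseases that this technology cannot screen.

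- **Adjustment.** Main model: age at blood collection (from birth date and collection time), sex, native place and instrument/reagent type, plus contributing unit if recorded. Further model: add gestational age, birth weight and feeding, noting that these may be on the causal path.
- **Groups.** Recessive: non-carrier, carrier, and biallelic (homozygous, or compound heterozygous with a stated class of second allele). Biallelic versus non-carrier is the main contrast; the carrier contrast is supportive only. Dominant: heterozygous or homozygous versus negative. X-linked: hemizygous versus negative males.
- **Error control.** State the significance level. List each gene's characteristic metabolite in advance as primary. Apply Benjamini-Hochberg across sites to the primary tests and, separately, to the remaining analytes. Describe this as false discovery rate control; it does not cap the chance of any false positive.
- **Small groups.** Report biallelic groups of fewer than about 5 descriptively, and do not read non-significance there as evidence of benignity.

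The cost is a paragraph, a gene-to-metabolite list and standard regression in the R version already named. The main-model covariates are in, or follow from, the section 3.3 list, except contributing unit, which is not named there. The downsides are fewer nominally significant analytes and slightly more analysis work. Medication, which section 1.1 names but section 3.3 item (3) does not list, would remain unadjusted.
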